8.3.7.1 Special Situation Reports

Special situation reports include reports of overdose, misuse, abuse, medication error, and reports of adverse reactions associated with product complaints.

- **Overdose:** Refers to the administration of a quantity of a medicinal product given per administration or cumulatively (accidentally or intentionally), which is above the maximum recommended dose according to the protocol. Clinical judgement should always be applied. In cases of a discrepancy in the drug accountability, overdose will be established only when it is clear that the patient has received additional dose(s) or the Investigator has reason to suspect that the patient has received additional dose(s).
- **Misuse:** Refers to situations where the medicinal product is intentionally and inappropriately used in a way that is not in accordance with the protocol instructions or local prescribing information and may be accompanied by harmful physical and/or psychological effects.
- **Abuse:** Is defined as persistent or sporadic, intentional excessive use of a medicinal product, which is accompanied by harmful physical or psychological effects.
- **Medication error:** Is any unintentional error in the prescribing, dispensing, or administration of a medicinal product by a healthcare professional, patient, or consumer, respectively. The administration or consumption of the unassigned treatment and administration of an expired

product are always reportable as medication errors; cases of patients missing doses of investigational product are not considered reportable as medication errors.

- **Product complaint:** Is defined as any written, electronic, or oral communication that alleges deficiencies related to the identity, quality, durability, reliability, safety, effectiveness, or performance of a drug or device after it is released for distribution. A Special Situations Report Form will only be completed if a complaint is associated with an adverse drug reaction.

All special situation events as described above must be reported on the Special Situations Report Form and faxed/mailed to [REDACTED] (contact information listed below) within 24 hours of knowledge of the event. All AEs associated with the Special Situations Report Form should be reported as AEs or SAEs as well as recorded on the AE eCRF and/or the SAE report form. Details of the symptoms and signs, clinical management, and outcome should be provided, when available.

Safety Contact Information:

8.4 Pharmacokinetics

Pharmacokinetic parameters are not evaluated in this study.

8.5 Genetics and/or Pharmacogenomics

Genetics are not evaluated in this study.

8.6 Biomarkers

Collection of biological samples for biomarker research is also part of this study. Urine samples for biomarker research are required and will be collected from all patients in this study as specified in the SoA (Section 1.3).

8.7 Immunogenicity Assessments

Immunogenicity assessments are not evaluated in this study.

8.8 Medical Resource Utilization and Health Economics

Medical Resource Utilization and Health Economics parameters are not evaluated in this study.

9 STATISTICAL CONSIDERATIONS

9.1 Statistical Hypotheses

No formal hypothesis testing is planned for this study.

9.2 Sample Size Determination

Note: “Enrolled” patients are those who have been randomized to a treatment arm.

No formal sample size determination was made for this study, whose primary endpoint is safety and tolerability. Approximately 60 patients will be randomized at approximately 38 clinical sites. Patients (n=20 in each arm) will be randomized to receive PSL [REDACTED] or placebo. [REDACTED]

Sample size estimates are based on a one-sided test at the 0.05 level to detect suppression of viral load to undetectable levels based on the viral load data from the CHARMS study of multivirus-specific T cells for patients with a plasma BK viral load <2000 copies/mL.

Patients will be stratified by screening BK viral load at randomization to ensure equal randomization among active and placebo arms for patient populations [REDACTED]
[REDACTED]

[REDACTED] A minimum of 6 patients must be enrolled in each stratum, but the remaining patients can be enrolled in either stratum.

9.3 Analysis Sets

For the purposes of analysis, the following analysis sets are defined:

Population	Description
Intent-to-Treat (ITT)	All randomized patients regardless of whether the patient receives PSL or placebo. Patients will be analyzed according to the randomized study treatment.
Safety	All randomized patients who receive PSL or placebo. All safety analyses will be based on the Safety Population. Patients will be analyzed according to the treatment actually received.

9.4 Statistical Analyses

The SAP will be finalized prior to database lock, and it will include a more technical and detailed description of the statistical analyses described in this section. This section is a summary of the planned statistical analyses of the most important endpoints including primary and key secondary endpoints.

9.4.1 General Considerations

Summary statistics will be presented by treatment group. Unless otherwise stated, continuous variables will be summarized using the number of non-missing observations, arithmetic mean, standard deviation, median, minimum, and maximum values as descriptive statistics. Categorical variables will be summarized using the frequency count and the percentage of patients in each category as descriptive statistics.

9.4.2 Primary Endpoint(s)

The primary endpoint is safety and tolerability, as assessed by a qualitative analysis of -treatment emergent adverse events (TEAEs) and changes in vital signs, physical examinations, clinical laboratory assessments, and ECGs.

9.4.3 Secondary Endpoints

The key secondary endpoint is change in BK viremia in patients receiving PSL compared to patients receiving placebo, based on quantitation of viremia performed at the central laboratory.

9.4.4 Tertiary/Exploratory Endpoint(s)

Exploratory continuous and categorical efficacy endpoints will be summarized descriptively by treatment group and dose cohort using the Intent-to-Treat (ITT) Population. Categorical endpoints will be summarized using number and percentage of patients within each category. For time-to-event variables, the Kaplan-Meier method will be used to estimate the median time (days) and its 95% confidence interval.

9.4.5 Safety Analysis

All safety data will be summarized by treatment arm actually received. Categorical endpoints will be summarized using number and percentage of patients within each category. Continuous endpoints will be summarized descriptively with summary statistics (number, mean, standard deviation, standard error, median, first quartile, third quartile, minimum, and maximum).

Adverse events will be coded using the Medical Dictionary for Regulatory Activities. A TEAE is defined as an AE with a start date and time on or after the first dose of study treatment and through the Week 24 visit. Treatment-emergent AEs will be summarized by System Organ Class and Preferred Term and further by severity (according to the National Cancer Institute [NCI] Common Terminology Criteria for Adverse Events [CTCAE] v5.0) and relationship to study treatment. The incidence of SAEs will be summarized.

The incidence of AESIs including acute GVHD, CRS, infusion reactions and their corresponding exact binomial confidence intervals with 95% confidence level will be presented by treatment group. Grading criteria for GVHD and CRS are in Appendix 5 in [Section 10.5](#) and Appendix 6 in [Section 10.6](#), respectively.

Descriptive statistics will be provided for relevant laboratory, vital sign, and ECG data. Abnormal laboratory results will be graded according to NCI CTCAE v5.0, if applicable. A shift table, presenting the 2-way frequency tabulation for baseline and the worst post-baseline value according to the NCI CTCAE grade, will be provided for selected clinical laboratory tests.

Clinical safety laboratory parameters will be presented in summary tables. Changes from baseline in laboratory parameters, vital sign parameters, and quantitative ECG parameters will be summarized. Selected laboratory parameters will be summarized in shift tables.

Statistical comparisons will be carried out using Fisher's exact test and Student's t test. A 1-sided $P < .05$ will be considered statistically significant. Key secondary outcomes such as BK viral load assessments and change in eGFR (measured by comparing the slope of decline in the eGFR over time) between the placebo group and treatment group will be analyzed using the statistical comparisons described above. The baseline demographics of patients, such as age and gender, etc., will also be analyzed to ensure adequate randomization.

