3 OBJECTIVES AND ENDPOINTS

Objectives	Endpoints
Primary 
 To compare the safety and tolerability of PSL to placebo in kidney transplant recipients 	
 Treatment-emergent adverse events (TEAEs) and changes in vital signs, physical exams, clinical laboratory assessments, and electrocardiograms (ECGs)
Key Secondary 
 To assess the overall efficacy of PSL to suppress plasma BK viral load compared with placebo 	
 Change in BK viremia in patients receiving PSL compared to patients receiving placebo
Other Secondary 
 To compare the relative efficacy of different dosing regimens of PSL to suppress BK viral load versus placebo 	
 Change in BK viremia in patients receiving different dosing regimens of PSL compared to patients receiving placebo
Exploratory 
 To assess change in estimated glomerular filtration rate (eGFR) over 24 weeks in recipients of PSL versus placebo 	
 Change in eGFR by Modified Dose in Renal Disease (MDRD) formula in recipients of PSL versus placebo

 To identify changes in donor-specific anti-human leukocyte antigen (anti-HLA) antibodies in recipients of PSL versus placebo 	
 Changes from baseline in levels of donor-specific anti-HLA antibodies in recipients of PSL versus placebo

 To determine the proportion of patients with resolution of BK viremia at 8 weeks post virus-specific T cell infusion 	
 Proportion of patients with resolution of BK viremia at 8 weeks post - Virus-Specific T cell infusion

 To assess kidney allograft survival at 24 weeks 	
 Proportion of patients with eGFR >20 mL/min at 24 weeks

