2 STUDY OVERVIEW

2.1 Study Objectives

2.1.1 Primary Objective

The primary objective is to compare the safety and tolerability of posoleucel (PSL, ALVR105, formerly Viralym-M) to placebo in kidney transplant recipients.

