3.5 Safety Analyses

Safety data will be summarized by treatment group (i.e., PSL, Placebo and Overall). Safety summary tables will be generated for actual treatment received, based on the Safety Population. The primary objective of the study is to assess the safety and tolerability of PSL in kidney transplant recipients based on TEAEs and changes in vital signs, physical examinations, clinical laboratory assessments, and ECGs. Categorical endpoints will be summarized using the number and percentage of patients within each category. Continuous endpoints will be summarized descriptively with summary statistics (number, mean, standard deviation, standard error, median, first quartile, third quartile, minimum, and maximum).

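### The primary objective compares safety with placebo, but no planned safety output gives a between-group difference or interval, and the protocol's undirected one-sided test rule does not fill the gap

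*Protocol*

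**What the plan says.** The objective is comparative in both documents. Protocol 3 has "To compare the safety and tolerability of PSL to placebo in kidney transplant recipients", and SAP 2.1.1 has "The primary objective is to compare the safety and tolerability of posoleucel", again against placebo.

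On method, the protocol says three different things:

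- Section 9.1: "No formal hypothesis testing is planned for this study".
- Section 9.4.2: the primary endpoint is safety and tolerability, "as assessed by a qualitative analysis of" adverse events and changes in safety measurements.
- Section 9.4.5, Safety Analysis: "Statistical comparisons will be carried out using" Fisher's exact and Student's t tests, followed by "A 1-sided $P < .05$ will be considered statistically significant". No direction is given. The next sentence applies these methods to key secondary outcomes, with BK viral load and eGFR as the examples. No safety endpoint is named. The same section promises 95% exact binomial intervals, by treatment group, for the incidence of AESIs (acute GVHD, CRS and infusion reactions).

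SAP 3.5 states "Categorical endpoints will be summarized using the number and percentage of patients within each category", with means, standard deviations, standard errors, medians, quartiles and ranges for continuous measures. Sections 3.5.1 to 3.5.5 add adverse event tables by severity and by relationship, changes from baseline, laboratory shift tables, potential Hy's Law counts and listings. They contain no test, no PSL-minus-placebo difference and no confidence interval. The AESI intervals are not carried over.

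**The concern.** A trial whose first objective is a comparison should produce an estimate of it with its uncertainty. Here the protocol's safety section offers a significance rule with no stated side, and the SAP offers adjacent columns to be read by eye. Neither tells the reader how much excess harm the data leave open. The only stated measure of safety precision, the exact AESI interval, is a per-group interval rather than a contrast, and the SAP loses even that.

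The undirected rule adds a second problem. If someone writing the study report takes its place under Safety Analysis at face value and applies it to adverse events, the result depends on a side that nobody has chosen. On either side, a P value above .05 could be misread as evidence of similar safety.

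**Working it through.** **Inputs.** Protocol 9.2 and SAP 2.2.3: 20 patients in each of three arms, so 3 × 20 = 60, and pooled PSL v placebo is 40 v 20. Protocol 9.4.5: one-sided 0.05, Fisher's exact test. The documents give no adverse event rate, margin, power or detectable difference for safety, so there is no safety figure of the plan's own to reproduce. The placebo rates below are assumptions, shown as a range.

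**Power if the rule were applied to a doubled event rate.** With a events among n1 PSL patients, b among n2 placebo patients and m = a + b, the one-sided Fisher P value towards harm is

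P(a,b) = Σ over k ≥ a of C(n1,k)·C(n2,m−k) / C(n1+n2,m).

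Power = Σ over all (a,b) of Bin(a; n1, 2p)·Bin(b; n2, p)·1[P(a,b) < 0.05], by full enumeration. For a test towards benefit, the P value sums over k ≤ a.

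| Assumed placebo rate | PSL rate | 40 v 20, towards harm | 20 v 20, towards harm |
|---|---|---|---|
| 5% | 10% | 3.6% | 2.0% |
| 10% | 20% | 13.6% | 10.9% |
| 15% | 30% | 23.1% | 19.8% |
| 20% | 40% | 35.1% | 29.0% |
| 25% | 50% | 47.8% | 37.5% |
| 30% | 60% | 62.1% | 46.3% |
| 40% | 80% | 87.8% | 75.3% |

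Power towards harm passes 50% at a placebo rate of about 26% (pooled) or 32% (single arm). If the test points towards benefit, the chance of flagging the doubling is at most 0.3% at every rate tried.

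**What an interval would show.** Take an illustrative 8/40 v 2/20, a difference of 20% − 10% = +10 points.

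- Fisher, towards harm: [C(40,8)·C(20,2) + C(40,9)·C(20,1) + C(40,10)] / C(60,10) = 0.28.
- Wilson 95% limits: 8/40 gives 0.105 to 0.348; 2/20 gives 0.028 to 0.301.
- Newcombe lower limit: 0.10 − √[(0.200 − 0.105)² + (0.301 − 0.100)²] = −0.12.
- Newcombe upper limit: 0.10 + √[(0.348 − 0.200)² + (0.100 − 0.028)²] = +0.26.

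The P value says only that the result is not significant. The interval, −12 to +26 points, says that an excess of up to about 26 points has not been excluded.

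**What the dropped AESI intervals would show.** With no events, the exact 95% upper limit is 1 − 0.025^(1/n): 16.8% for n = 20 and 8.8% for n = 40. Tables reporting 0% without these limits hide that margin.

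**The case against.** A reader might infer that, under this plan, a doubled serious adverse event rate would usually be reported as no difference. The documents do not support that. It would require the Fisher test to be applied to serious events, to point towards harm, and to have a non-significant result read as equivalence. Protocol 9.4.5 says only that the incidence of serious events will be summarized; the outcomes it names for the tests are BK viral load and eGFR; 9.1 plans no formal testing; and the SAP contains no safety test, so under the SAP there would be no safety P value to misread. 'Usually' also depends on an assumed placebo rate below about 26%. Nor is the SAP limited to counts: it includes continuous summaries, changes from baseline and shift tables.

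Low power is not itself a fault. This is a proof-of-concept study with no formal sample size for safety. Descriptive safety reporting in 60 patients is a legitimate choice, and safety is also protected by a DSMB with an unblinded statistician and by the rule in Protocol 9.5.1.2 that halts randomization after three qualifying related serious events.

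All of this stands, and it narrows the point to two things: the missing comparative estimate, and the conflict between the sections. Monitoring protects patients during the trial, but it does not supply the comparison that the final report owes its primary objective. A descriptive analysis can include a difference and an interval without becoming a test.

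**Conclusion.** The point holds in this form. The primary objective is comparative, the SAP plans no between-group safety estimate or interval, and it drops the AESI intervals that the protocol promises. Protocol 9.1, 9.4.2 and 9.4.5 do not agree on whether anything is tested, and 9.4.5 leaves both the scope and the direction of its rule open.

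The power figures, 4% to 88% across placebo rates of 5% to 40%, describe what the rule would do if it were used for adverse events. They rest on assumed rates, a true doubling and a 40 v 20 split. They show that the rule is a poor substitute for an estimate; they do not describe an analysis that the SAP plans, and they are not an argument for a larger trial.

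**What to change.** - Reconcile Protocol 9.1, 9.4.2 and 9.4.5 with SAP 3.5 and 3.5.1. State that the one-sided rule does not apply to safety. Restrict the sentence rather than simply deleting it, because it also governs BK viral load and eGFR.
- In SAP 3.5.1, add the PSL-minus-placebo risk difference with a two-sided 95% Newcombe or Miettinen-Nurminen interval for a short fixed list: any TEAE, Grade 3 or higher TEAE, treatment-emergent serious event, related TEAE, AESI, and TEAE leading to discontinuation of study treatment.
- Give the pooled contrast first, with each PSL arm v placebo as supportive. That is 6 endpoints × 3 contrasts = 18 intervals, so label them descriptive and unadjusted for multiplicity.
- Restore the 95% exact intervals for AESI incidence by group.
- State that a wide interval or a non-significant result is not evidence of similar safety.

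The cost is a few extra table columns. The by-arm contrasts need somewhat more, because SAP 3.5 groups safety as PSL, placebo and overall. No new data are needed and trial conduct does not change. The readout will look less reassuring, because the intervals will be wide.

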9.4.6 Other Analyses

In addition to the endpoints described previously, the following endpoints may be analyzed:

- Frequency and severity (adjudicated Banff classification) of biopsy-proven acute allograft rejection in recipients of PSL versus placebo.
- Number of patients in the investigational arms with polyomavirus haufen in the urine as compared to the placebo arm.
- Quantification of IFN- γ (+) T cells specific for BK virus in patients in the investigational arms as compared to the placebo arm.
- Levels of (virus-specific T cell) donor T cell deoxyribonucleic acid (DNA) as compared to patient T cell DNA in peripheral blood.
- Time to resolution of non-BK target viral infections (ie, associated signs, symptoms, and presence/absence of HHV-6, EBV, JCV, and/or AdV viremia) present at the time of randomization.
- Use of immunosuppressive agents, including specific immunosuppressive agents used, dosed, and any changes in dose.
- Number of hospitalizations/re-hospitalizations for any reason and number of days.
- Incidence and duration of use of any other antiviral therapies during the study.
- Time to death (from any cause) from the time of randomization.
- Number of patients with kidney injury requiring hemodialysis.
- Rate of decline of BK viremia in recipients of PSL using different dosing intervals versus that in patients receiving placebo.
- Assessment of renal function (eGFR estimated by the creatinine-cystatin C method).

Details of these analyses are provided in the SAP.

9.5 Interim Analyses

Administrative interim analyses are planned for the study. The Sponsor's study team and Investigators will remain blinded to individual patient data during and after the administrative interim analyses. All administrative interim analyses will be conducted by the Sponsor.

- The first administrative interim analysis will be performed by the Sponsor when 12 patients in Stratum 1 [REDACTED] have completed 8 weeks in the study.
- The second administrative interim analysis will be performed when 30 patients have completed 8 weeks in the study.
- Interim analyses may be omitted or added at the discretion of the Sponsor to allow for long term planning, and to assess ending the study or either arm early.

9.5.1 Stopping Criteria

9.5.1.1 Stopping Criteria for Individual Patients

As GVHD and CRS are theoretical safety concerns associated with administration of third-party allogeneic T cells, the incidence and severity of GVHD and CRS will be monitored during the study.

No patients will be permitted to receive a second infusion of PSL or placebo if they develop new onset GVHD \geq Stage 1 or CRS Grade >2 at the proposed time of infusion of any subsequent dose.

After the first 3 doses, patients who have undetectable BK plasma viral load at 2 or more consecutive assessments at least 2 weeks apart will discontinue PSL infusions.

9.5.1.2 Stopping Criteria for the Study

Randomization into the study will be halted if 3 patients experience SAEs that meet the following criteria:

- \geq CTCAE Grade 3,
- Considered related by the Investigator,
- Occur during Period 1 following the initial dose, AND
- Cannot be reasonably attributed to the patient's underlying disease, other medical condition, or concomitant medications.

If this occurs, randomization will not resume until the DSMB has thoroughly reviewed all safety data to date and concluded that it is safe for the study to continue.

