Administrative interim analyses are planned for the study. The Sponsor's study team and Investigators will remain blinded to individual patient data during and after the administrative interim analyses. The first interim analysis will be performed by the Sponsor when 12 patients in Stratum 1 have completed 8 weeks in the study, and the second interim analysis will be performed when 30 patients have completed 8 weeks in the study. Interim analyses may be omitted or added at the discretion of the Sponsor to allow for long term planning, and to assess ending the study or either arm early, as described in the statistical analysis plan (SAP). See [Figure 1](#) for a schematic representation of the study design.

Stopping rules for each dosing interval arm and for the study are detailed in [Section 9.5.1](#).

After the ~~first~~ 3 doses, patients who have undetectable BK plasma viral load at 2 or more consecutive assessments at least 2 weeks apart will discontinue PSL infusions. If a patient's viral load becomes undetectable, such a patient may be followed every 14 days for study evaluations as per the Schedule of Activities ([Section 1.3](#)). No patients are permitted to receive a subsequent infusion of PSL if they develop new onset GVHD (\geq Stage 1; see Appendix 5, [Section 10.5](#)) or cytokine release syndrome (CRS) ($>$ Grade 2; see Appendix 6, [Section 10.6](#)) at the proposed time for infusion of any subsequent dose.

An independent Data and Safety Monitoring Board (DSMB) will be convened for this study to routinely monitor patient safety and evaluate prespecified interim analyses to stop the study early (see [Section 10.1.5](#)).

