7 DISCONTINUATION OF STUDY TREATMENT AND PATIENT DISCONTINUATION/WITHDRAWAL

7.1 Discontinuation of Study Treatment

The following criteria do not necessitate withdrawal from the study, but do render the patient ineligible to receive any additional infusions of study treatment:

1. Development of \geq Grade 1 acute GVHD within 6 weeks, or a Grade 3 to 4 non-hematologic AE within 4 weeks from last PSL dose that is considered related to study treatment administration. If this occurs, the patient's toxicities will be followed until resolution or until the patient's participation in the study ends.
2. Receipt of any other hematopoietic stem cell product.
3. Receipt of therapy for new malignancy.
4. Occurrence of Grade 3 or 4 CRS. If this occurs, the patient's toxicities will be followed until resolution or until the patient's participation in the study ends.
5. Requirement for prohibited concomitant medication
6. Pregnancy

If any of the above criteria are met, every effort should be made to keep the patient in the study and continue follow-up.

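### The study stopping rule acts only on randomization, so it states no action after the last patient is randomized and nothing on ongoing infusions; the arm-level rules that Protocol 4.1 places in 9.5.1 are not there

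*Protocol*

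**What the plan says.** Protocol 9.5.1.2 (Stopping Criteria for the Study) states: "Randomization into the study will be halted if 3 patients experience SAEs that meet the following criteria". An event must be CTCAE Grade 3 or higher, judged related by the investigator, and not reasonably explained by underlying disease, another condition or concomitant medication. The timing condition reads "Occur during Period 1 following the initial dose, AND". Patients are counted across the study, not by arm. Once the halt is in force, "randomization will not resume until the DSMB has thoroughly reviewed all safety data to date" and found that the study can safely go on. The section gives no other action.

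Protocol 4.1 tells the reader: "Stopping rules for each dosing interval arm and for the study are detailed in" Section 9.5.1. That section has two parts, 9.5.1.1 for individual patients and 9.5.1.2 for the study. Neither contains an arm-level criterion, and neither shows a redaction mark.

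Protocol 9.5, Protocol 10.1.5.1 and SAP 3.6 all mention ending one arm early, without a criterion. SAP 2.2.1 refers to a Section 3.7 for the interim analyses, but the SAP text available goes from 3.6 straight to the appendices.

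**The concern.** The heading of 9.5.1.2 and the conclusion that it asks of the DSMB both concern the whole study. The action concerns only patients not yet randomized. Two groups are left without a stated provision: patients partway through their infusions when the third event occurs, and all patients still being dosed after enrolment closes, when a randomization halt has nothing to act on.

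This matters because safety is the primary endpoint (Protocol 9.4.2) and Protocol 4.3 says there is no experience with the product in solid organ transplant. The cross-reference in 4.1 adds a second problem: a reader who relies on it will believe that each dosing arm has its own stopping criterion and will find none.

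**Working it through.** **Text check.** Four provisions, side by side:

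- Events that count: any in Period 1 after the first dose (9.5.1.2). For the last patient randomized, that window runs to about 12 weeks after randomization closes.
- Action: halt randomization (9.5.1.2). Once the last patient is randomized, there is nothing to halt.
- DSMB review: stated only as the condition for resuming randomization (9.5.1.2). With no halt, it is not called for.
- Stopping of dosing: 9.5.1.1 (GVHD, CRS, viral clearance) and 7.1, which covers among other things "a Grade 3 to 4 non-hematologic AE within 4 weeks from last PSL dose that is considered related to study treatment administration". Each acts only on the patient concerned.

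The plan gives no operating characteristics for the rule, so there is no figure to reproduce. What follows shows scale only; the finding does not depend on it.

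**Inputs from the documents.** About 60 patients, 20 per arm (Protocol 9.2); enrolment over about 12 months and 12 weeks of treatment (Protocol 4.1); eight infusion visits, at Day 1 and Weeks 1, 2, 4, 6, 8, 10 and 12 (Protocol 1.3, Table 1).

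**Assumptions not in the documents.** Uniform accrual; no early stopping for viral clearance; a per-patient probability of a qualifying SAE of 5% to 20%, equal in all arms; event times uniform over the 12 weeks.

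**Patients on study treatment at one time.** 60/365 × 84 = 13.8, about 14.

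**Infusions after the last randomization.** An infusion at week w falls after the last randomization for patients enrolled in the final w weeks, about 60 × w/52 of them. The weeks sum to 0+1+2+4+6+8+10+12 = 43, so the count is 60 × 43/52 = 49.6 of 60 × 8 = 480, or 10.3%. Placing 60 patients at equal intervals over 365 days gives 53 of 480 (11.0%), in 14 patients. With 6-month accrual the equal-interval count is 102 (21%) in 28 patients; with 18 months it is 37 (8%) in 10.

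**PSL infusions only.** SAP 2.2.3 gives PSL every 14 or 28 days after three weekly doses. The 14-day arm contributes 20 × 43/52 = 16.5. For the 28-day arm, PSL at weeks 0, 1, 2, 6, 10 (sum 19) gives 7.3, and at weeks 0, 1, 2, 4, 8, 12 (sum 27) gives 10.4. Which placement applies is assumed. The total is about 24 to 27.

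**Chance of reaching the trigger.** With X binomial (60, p), P(X ≥ 3) is 0.58 at p = 5%, 0.95 at 10% and 0.996 at 15%.

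**Share of triggers that fall after the last randomization**, among trials that reach the trigger (40,000 simulated trials per cell):

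| Accrual | 5% | 10% | 15% | 20% |
|---|---|---|---|---|
| 6 months | 32% | 11% | 2.3% | 0.4% |
| 12 months | 16% | 4.7% | 0.8% | 0.1% |
| 18 months | 11% | 3.1% | 0.4% | 0.1% |

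As a share of all trials, the 12-month figures are 0.59 × 16% = 9.4% at a 5% event rate and 0.947 × 4.7% = 4.5% at 10%.

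**Trigger during enrolment, 12-month accrual.** Across the four event rates, 12.1 to 13.1 event-free patients are on treatment when the rule triggers, with 45.5 to 47.4 scheduled infusions ahead that 9.5.1.2 does not address.

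**The case against.** The best defence is that 9.5.1.2 does not stand alone. Protocol 7.1 ends dosing for a patient with a related severe non-hematologic event. Protocol 8 sends immediate safety concerns to the sponsor at once. SAEs are reported within 24 hours (8.3.2 follows on from 8.3.1, which sets that limit). The DSMB monitors safety routinely and receives summaries of unexpected SAEs (10.1.5.1), and the sponsor may close the study whenever it chooses (10.1.9). A study-level criterion may also legitimately act through randomization, and the DSMB's conclusion already concerns the whole study.

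Much of this stands. A reader might infer that patients on treatment must keep being infused after the third event; the protocol is silent and orders no such thing. A reader might also infer that safety oversight ends with enrolment; it does not. What the defence does not supply is a stated consequence of the third event once randomization is closed. Routine monitoring has no stated frequency, and the summaries cover unexpected SAEs, whereas 9.5.1.2 counts related Grade 3 or higher SAEs whether expected or not.

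On arm-level rules, the DSMB charter is a separate document and may contain them, so the documents do not show that such rules do not exist. The phrase in 4.1 may also be leftover wording: the synopsis sentence mentions only rules for the study, and 4.1 still refers to a Cohort A. Either way, the cross-reference to 9.5.1 is wrong as it stands.

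On size, the infusion counts include placebo, would be lower with stopping for viral clearance, and are not the chance that the rule fails to act. The simulated shares come closer to that.

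**Conclusion.** The concern holds as a gap in 9.5.1.2 and a contradiction between 4.1 and 9.5.1. It does not show that dosing is required to continue, that arm-level rules are absent from every trial document, or that patients would be unmonitored.

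The late-trigger gap is modest under the planned 12-month accrual. It is largest where qualifying events are uncommon or accrual is fast, and nearly vanishes at event rates of 15% or more. The silence on ongoing infusions is wider, because it applies whenever the rule triggers while patients are on treatment. Both parts follow from the text; the percentages rest on assumed event rates, uniform accrual and full dosing. The correction should be made: this is the only study-level safety trigger in the two documents, and the remedy is cheap.

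**What to change.** - Reword 9.5.1.2 so that the DSMB review it already requires follows the third qualifying SAE whether or not randomization is open.
- Reconcile the heading, the action and the DSMB conclusion in 9.5.1.2 so that the section states what applies to ongoing infusions during that review. The clinical team and the DSMB decide the content.
- Reconcile 4.1 with 9.5.1, 10.1.5.1 and SAP 3.6: either point to the document that holds the arm-level criteria or remove the statement from 4.1. Correct the SAP 2.2.1 reference to Section 3.7 at the same time.

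The cost is a protocol clarification, matching wording in the DSMB charter, and at most one extra DSMB meeting. Sample size, visits and analyses do not change.
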